# AEs related to Pexa-Vec

AEs related to Pexa-Vec are the AEs with the item "Is this event related to Pexa-Vec?" ticked "Yes" in "Adverse Event" form of the eCRF. If the data is missing, the AE will be considered as related to Pexa-Vec.

## AEs related to Nivolumab

AEs related to Nivolumab are the AEs with the item "Is this event related to Nivolumab?" ticked "Yes" in "Adverse Event" form of the eCRF. If the data is missing, the AE will be considered as related to Nivolumab.

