## 2.1 Phase I

The Phase I part is a single cohort enrolling 6 patients at standard Pexa-Vec and nivolumab doses, i.e.  $1x10^9$  pfu and 240 mg, respectively.

Pexa-Vec will be administered by intra-tumoral infusion on D1, D15 and D29, and nivolumab by intravenous infusion on D15 and D29 and then every two weeks. The study will document dose-limiting toxicities (DLTs) and landmark AEs. A landmark AE is an anticipated effect of the combination defined as an increase in severity of hepatic cytolysis (doubling of AST – ALT baseline blood concentrations), or significant deterioration of hepatic function (INR, bilirubin), or increase in incidence or severity of immune-related AEs, or increase in number or severity of Pexa-Vec-related skin lesions.

The first patient will be monitored for the safety scheduled up to D29, i.e. the end of the DLT monitoring period, before 5 additional patients can be enrolled. In addition, a security time interval of 2 weeks between enrolments of consecutive patients will apply. This time interval is appropriate to prevent additional patients to be exposed to potential acute or subacute toxic events observed in the previous patients.

If more than one DLT is observed in the first 6 patients, or in case of the occurrence of a landmark AE, one de-escalation dose regimen will apply on a cohort of 6 additional patients. Depending on the DLT profile relative to the known toxicity of each component of the combination and upon the recommendation of the Independent Safety Committee (ISC), the doses of Pexa-Vec and nivolumab will be either  $3x10^8$  pfu for Pexa-Vec and 240 mg q2 weeks for nivolumab OR  $10^9$  pfu for Pexa-Vec and 240 mg q3 weeks for nivolumab

In case no more than one DLT and no occurrence of any landmark AE is observed in 6 patients at the initial Phase I dose level or, if relevant, at the de-escalation dose level, the Phase IIa part of the study could start.

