## 5.2 Duration of Treatment

Patients of Phase I and Phase IIa will receive intratumoral (IT) injections of Pexa-Vec in combination with nivolumab intravenous (IV) infusions:

- Pexa-Vec injections will be performed on D1, D15 and D29. Additional Pexa-Vec boosts
  may be performed from Week 12 after discussion on a case by case basis between the
  investigator and Transgene, on the grounds of individual patient benefit.
- Nivolumab will be given from D15 every 2 weeks as long as a clinical benefit is observed with no unacceptable toxicity.

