# 6.1 Subject populations

## Safety population

All patients enrolled into the study who received at least one dose of either IMP will be included in the safety analysis. The patients will be analyzed according to the treatment actually received (Pexa-Vec or Pexa-Vec + Nivolumab) and this population will be the primary dataset for safety evaluation.

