## 7.6 Missing data

Measurements that were not performed or not recorded are treated as missing data.

No imputation will be done for missing data, excepted for calculation of duration with missing and incomplete dates for birth and adverse events (AE). Missing data will be noted as missing in appropriate tables/listings.

Imputation Rules for Partial Birthdates:

- If the month and year are present, impute the day by the 15th day of that month.
- If only the year is present, impute by July 1st of that year.

Imputation Rules for Partial or Missing Start Dates for AE:

- If the month and year are present, impute the day by the first day of that month. If the month and year are the same as those of the date of first dose of IMP, impute the day with the day of first treatment administration.
- If only the year is present, impute by January 1st. If the year is the same as the year of the date of first dose of IMP, impute by the date of first treatment administration.
- If the start date is entirely missing, impute by the date of first treatment administration.

Imputation Rules for Partial or Missing Stop Dates for AE:

- If the month and year are present, impute the day by the last day of that month.
- If only the year is present, impute by December 31st of that year.
- If the stop date is entirely missing, assume the event is ongoing.

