#### 8.8.1 Adverse Events

#### 8.8.1.1 Definitions

From the date of signature of ICF and up to first IMP administration (i.e. before the patient receives any IMP) only SARs caused by a protocol-required procedure (e.g., related to invasive procedures such as blood sampling) will be collected and reported. AEs, SAEs, or procedure related ARs that occur during this period, and that are considered by the investigator as relevant to the patient condition, will be collected as a current medical history.

After the initiation of either IMP and up to 28 days after the last dose of IMP, all AEs and SAEs will be collected and recorded on the eCRF. SAEs will also be reported to Transgene.

SAEs occurring more than 28 days after the last dose of IMP, and evaluated by the Investigator as related to the IMP will be collected and reported to Transgene indefinitely even after end of study. Only SAEs occurring prior to end of study will be reported in the eCRF.

All AEs will be coded using the Medical Dictionary for Regulatory Activities (MedDRA) central coding dictionary using latest version available. NCI-CTCAE version 4.03, dated June 14, 2010 will be used.

All AEs will be reported on the "Adverse Event" section of eCRF.

Dose-limiting toxicity (DLT) is defined as any of the following treatment-related adverse events (AEs) and occurring during the first 4 weeks (up to D29), in the Phase I part of the study; grades are referring to NCI CTCAE v. 4.03:

- 1. All Grade 3-4 non-hematologic toxicity that represent a 2-grade increase over baseline, excluding:
  - Untreated or inadequately treated nausea, vomiting and diarrhea,
  - Untreated or inadequately treated fever > 40.0°C lasting less than 24 hours (Grade
     3); only fever > 40.0°C lasting more than 24 hours (Grade 4) qualifies for DLT
  - Alopecia,
  - Grade 3 fatigue that returns to grade 2 or less within 7 days.
  - Grade 3 laboratory/metabolic abnormalities, other than ALT or AST, that are not considered clinically significant and that return to grade 2 or less within 72 hours.
- 2. Any Grade ≥ 3 treatment-related acute immune-related AE involving major organs, such as: immune-related pneumonitis, colitis, nephritis, hepatitis, endocrinopathies, immune-related rash and other rare but severe immune-related reactions.

- 3. Grade  $\geq$  3 injection site reaction.

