#### 8.8.1.4 Tables

An overview table will be presented by Cohort (Cohort#1, Cohort#-1 and overall) with the number and percentage of patients for each of the following categories (the number of events will be also provided) with at least:

- one AE
- one AE subject to immediate reporting
- one dose limiting toxicity AEs
- one immune-related AEs
- one AEs related to IMP
- one AEs related to Pexa-Vec
- one AEs related to Nivolumab
- one AEs related to study procedure
- one AEs leading to treatment discontinuation
- one AEs related to IMP and leading to treatment discontinuation
- one SAE
- one SAEs related to IMP
- one grade 3/4/5 AEs
- one grade 3/4/5 AEs related to IMP
- one grade 3/4/5 AEs related to IMP leading to treatment discontinuation

The number and percentage of patients for each category above will be summarized by Cohort (Cohort#1, Cohort#-1 and overall) in a frequency table by body system organ class (SOC) and preferred terms (PT) as per MedDRA dictionary. The number of events will be also summarized in the same table.

Table for AEs, AEs related to IMP, AEs related to Pexa-Vec and AEs related to Nivolumab will also be presented by grade and summarized by Cohort (Cohort#1, Cohort#-1 and overall) in a frequency table by SOC and PT as per MedDRA dictionary.

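### A blank nivolumab causality answer counts as nivolumab-related even for an AE that began before any nivolumab was given, and the AE tables described do not separate the Pexa-Vec-only lead-in

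*SAP*

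**What the plan says.** The schedule is in SAP section 5.2: "Pexa-Vec injections will be performed on D1, D15 and D29", and "Nivolumab will be given from D15 every 2 weeks". SAP section 2.1 agrees for Phase I: "nivolumab by intravenous infusion on D15 and D29 and then every two weeks". AE collection starts with whichever product comes first (SAP section 8.8.1.1): "After the initiation of either IMP and up to 28 days after the last dose of IMP, all AEs and SAEs will be collected".

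SAP section 8.8.1.2 then sets the rule for a missing nivolumab causality answer: "If the data is missing, the AE will be considered as related to Nivolumab". A parallel rule covers Pexa-Vec. An AE counts as related to IMP if it is related to either product or to both.

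Protocol section 10.2 defines related and not related partly by the time relation between the event and dosing. SAP section 8.8.1.3 lists each AE with its onset as a study day and shows the nivolumab relation as Related or Not Related only.

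On layout, SAP section 8.8.1.4 states: "An overview table will be presented by Cohort (Cohort#1, Cohort#-1 and overall"; the SOC/PT and grade tables follow the same columns. SAP section 6.1 says safety patients are analysed "according to the treatment actually received (Pexa-Vec or Pexa-Vec + Nivolumab"). Protocol section 12.3.2 names time dependence among the factors to examine, as appropriate, for common AEs.

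**The concern.** Treating a missing answer as related is a reasonable conservative default for a patient who has received the drug. Before the first infusion it is not conservative, because it asserts something that cannot be true.

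Attribution to each component matters here. Safety of the combination is the Phase I primary objective. The two de-escalation options in SAP section 7.2 each change a different component, and the choice looks to the known toxicity of each. A table of nivolumab-related AEs that includes events from before nivolumab is a poor basis for that discussion.

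The layout question is separate and does not depend on missing answers. In a single-arm trial the first fortnight is the planned period on Pexa-Vec alone. Tables by cohort merge it with everything that follows, so a reader cannot see from a summary which AEs arose before nivolumab was added.

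**Working it through.** The plan gives no figure on this point to reproduce. The check is mainly a reading of the rules side by side, with illustrative arithmetic for size.

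**1. Length of the lead-in.** The inputs are first Pexa-Vec on D1 and first nivolumab on D15 (SAP section 5.2), the ±1 day visit window (Protocol section 8.5), and a DLT period from D1 to D29 (Protocol section 10.1).

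- Days before nivolumab: 15 − 1 = 14.
- Share of the 29 days D1 to D29: 14/29 = 48%. With the visit window it is 13/29 = 45% to 15/29 = 52%.

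This is a share of days, not of AEs.

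**2. One AE followed through the rules.** Take a fever with onset on D2 and a blank nivolumab answer. It is collected, because Pexa-Vec has been given. The default makes it nivolumab-related, although the first infusion is 15 − 2 = 13 days away. Under Protocol section 10.2 that timing would point to not related. The same default for Pexa-Vec cannot produce this result, because Pexa-Vec is the first product given and collection starts with it.

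**3. Effect on the IMP-related count.** For an AE before D15 with a blank nivolumab answer:

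| Pexa-Vec answer | IMP-related without the nivolumab default | IMP-related with it |
|---|---|---|
| Yes | Yes | Yes |
| Blank (default: related) | Yes | Yes |
| No | No | Yes |

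Only the last row changes. The nivolumab-specific tables change in all three.

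**4. Size.** Let f be the share of AEs that start before D15, and m the share of those with a blank nivolumab answer. AEs wrongly labelled nivolumab-related per 100 AEs = 100 × f × m. The documents give neither f nor m, so these values are assumptions.

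| m | f = 10% | f = 25% | f = 50% |
|---|---|---|---|
| 0% | 0 | 0 | 0 |
| 1% | 0.1 | 0.25 | 0.5 |
| 5% | 0.5 | 1.25 | 2.5 |
| 10% | 1 | 2.5 | 5 |
| 100% (extreme) | 10 | 25 | 50 |

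The extreme row would apply only if sites routinely left the nivolumab question empty before D15. The listing shows no value for not yet exposed, but the form itself is not available, so this cannot be checked.

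**5. Table layout.** SAP section 8.8.1.4 describes tables by cohort, category, SOC/PT and grade. None uses onset relative to first nivolumab. The wording on treatment received in SAP section 6.1 would separate patients who never had nivolumab from those who did. It would not separate the first fortnight from later time within a patient.

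**The case against.** The other side has good points.

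- **Few blanks are likely.** Protocol section 17.2 requires source verification of every item. SAP section 7.4 has draft outputs reviewed for missing critical data, and SAP section 7.5 has a data review meeting on completeness. This stands, and it is why the likely size is small. It does not make the rule correct.
- **Early AEs belong in the safety profile.** The Pexa-Vec priming injection is part of the regimen and the DLT period starts on D1. This stands: the early AEs should stay in the tables, and the request is only to show them separately as well.
- **Other routes exist.** There are separate tables for Pexa-Vec-related and nivolumab-related AEs, and the listings carry onset day. The first depends on the causality answers at issue. The second allows a hand count but is not a planned summary.
- **The Section 10 table list is not visible in the public text.** This stands. The layout point covers only the tables described in SAP section 8.8.1.4.

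Three stronger inferences are tempting, and the documents do not support them.

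- **Date imputation moves nivolumab reactions into the lead-in.** SAP section 7.6 does say "If the start date is entirely missing, impute by the date of first treatment administration", but it restricts imputation to the calculation of durations. No table described in SAP section 8.8.1.4 uses onset date, so none is distorted. The issue would arise only once a split by onset is added.
- **The immune-related flag is the one item without a missing-data default.** It has none, but neither do immediate reporting, treatment discontinuation or death.
- **The default drives DLT or de-escalation decisions.** DLT is a separate listed item, and nothing shows that this rule feeds it.

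**Conclusion.** Two limited points hold.

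First, the default for a blank nivolumab answer lacks an exposure condition and can label an AE nivolumab-related before any exposure, contrary to the protocol's own view of causality. The error inflates the nivolumab-specific tables. Its size rests on the assumed f and m and is probably small, and it is nil if no early answer is blank.

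Second, the described AE tables do not separate the lead-in, although the SAP refers to treatment received and the protocol to time dependence. This touches the presentation of every D1 to D14 AE, whatever the missing rate.

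A reader might conclude that the safety profile of the combination as a whole is misattributed. That goes too far, because relatedness to IMP is a union and moves in only one of the three cases above. The matter is minor to moderate, and worth correcting because the correction is cheap.

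**What to change.** **SAP section 8.8.1.2.** Apply the missing-means-related default for nivolumab only to AEs with onset on or after that patient's first nivolumab infusion, or with an onset that cannot be placed before it. Code AEs known to have started earlier as not related (not yet exposed). Report the number of causality answers imputed.

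**SAP section 8.8.1.4.** Add an AE overview and a SOC/PT summary by onset before, versus on or after, first nivolumab. Use recorded rather than imputed onset dates. Show AEs whose period cannot be determined in a column of their own. Give exposure time for each period, because the first lasts about two weeks and the second can last much longer.

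**Cost.** SAP wording and a little extra table programming, with no new data. The period comparison must be labelled descriptive. Protocol section 8.1 expects reactions to weaken at later injections, so first-injection effects are confounded with the absence of nivolumab.

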# AEs related to IMP (Pexa-Vec + Nivolumab)

AEs related to IMP are the AEs related to either Pexa-Vec or Nivolumab (or both).

## AE leading to treatment discontinuation

AE leading to discontinuation are the AEs with the items "Action taken with Pexa-Vec" or "Action taken with Nivolumab" ticked "Drug withdrawn".

#### Immune-related AEs

Immune-related AEs are the AEs with the item "Is this event immune related?" ticked "Yes".

## AE leading to death

The AE leading to death are the AEs with the item

• "Toxicity grade" ticked "Grade 5 or Fatal" or

"Outcome" ticked "Fatal"

## **8.8.1.3** Listings

All AEs will be listed with the following items:

- Patient Number
- Cohort (Cohort #1 and Cohort #-1)
- Age / Gender
- Verbatim, PT and SOC
- Date of onset and date of end (study day)
- Duration of the AE in days
- Toxicity grade (Grade 1 / Grade 2 / Grade 3 / Grade 4 / Grade 5)
- Outcome (Recovered / Recovered with sequelae / Not recovered / Fatal / Unknown)
- Relation to Pexa-Vec (Related/Not Related) and Action taken regarding Pexa-Vec
- Relation to Nivolumab (Related/Not Related) and Action taken regarding Nivolumab
- Relation to Study Procedure (Related/Not Related)
- Action regarding the event (None / Medication given / Procedure implemented/Early study termination/ Required Hospitalization)
- Evaluation of seriousness
- Dose-limiting toxicity (Y/N)
- Event immune related (Y/N)
- AE subject to immediate reporting
- DLT population flag (Y/N)
- PP population flag (Y/N)

Moreover, the following sub-listings will be provided:

- AEs subject to immediate reporting
- Dose-limiting toxicity AEs
- IMP-related AEs

- Immune-related AEs
- SAEs
- IMP-related SAEs
- AEs leading to treatment discontinuation
- Grade 3/4/5 adverse events
- Fatal AEs

#### 8.8.1.4 Tables

An overview table will be presented by Cohort (Cohort#1, Cohort#-1 and overall) with the number and percentage of patients for each of the following categories (the number of events will be also provided) with at least:

- one AE
- one AE subject to immediate reporting
- one dose limiting toxicity AEs
- one immune-related AEs
- one AEs related to IMP
- one AEs related to Pexa-Vec
- one AEs related to Nivolumab
- one AEs related to study procedure
- one AEs leading to treatment discontinuation
- one AEs related to IMP and leading to treatment discontinuation
- one SAE
- one SAEs related to IMP
- one grade 3/4/5 AEs
- one grade 3/4/5 AEs related to IMP
- one grade 3/4/5 AEs related to IMP leading to treatment discontinuation

The number and percentage of patients for each category above will be summarized by Cohort (Cohort#1, Cohort#-1 and overall) in a frequency table by body system organ class (SOC) and preferred terms (PT) as per MedDRA dictionary. The number of events will be also summarized in the same table.

Table for AEs, AEs related to IMP, AEs related to Pexa-Vec and AEs related to Nivolumab will also be presented by grade and summarized by Cohort (Cohort#1, Cohort#-1 and overall) in a frequency table by SOC and PT as per MedDRA dictionary.

## 8.8.2 Laboratory abnormalities

Listings of laboratory data will be provided by visit and displaying the Standard International (SI) units converted laboratory parameters with at least value, change from baseline, reference range, high/low, grade (if applicable) and clinical significance.

Laboratory data will be summarized at baseline by presenting descriptive statistics for all hematology and biochemistry parameters. All values will be displayed in SI units. A dedicated listing will be done for AFP results (reported in ng/mL).

Laboratory parameters (hematology and biochemistry) will be graded using the NCI-CTCAE version 4.03, dated June 14, 2010. A shift table of baseline CTCAE grade versus worst CTCAE grade during study will be presented for hematology and biochemistry parameters by Cohort (Cohort#1, Cohort#-1 and overall). For parameters with two directions abnormalities (decrease/increase), two shift tables will be presented. The list of laboratory parameters and their abnormalities graded according to CTCAE are presented in section 11.

## 8.8.3 Other safety data

# Vital signs collected during and up to 24h after IMP administration

All vital signs collected during and up to 24h after IMP administration (either Pexa-Vec or Nivolumab) will be listed for each patient and visit administration.

## Vital signs and physical examinations

All vital signs (SBP and DBP in mmHg, heart rate in bpm, respiratory rate in bpm, temperature in °C, body weight in kg and BMI in kg/m²) and physical examinations will be listed by patients. All these results will be presented for SAF and DLT populations for Phase I and for SAF population for Phase IIa by cohort.

#### Thyroid function

Thyroid function will be listed by patients. All these results will be presented for SAF and DLT populations for Phase I and for SAF population for Phase IIa by cohort.

#### **ECOG**

ECOG performance status will be listed by patients. All these results will be presented for SAF and DLT populations for Phase I and for SAF population for Phase IIa by cohort.

[figure not shown]
## Electrocardiogram, echocardiogram and Troponin levels

All electrocardiogram results performed during the study will be listed for SAF population (all abnormalities will be listed).

Results of echocardiogram (Left Ventricular Ejection Fraction expressed in percentage) and Troponin levels (Troponin I and Troponin T, expressed in ng/mL) will be listed together for SAF population. Results of echocardiogram will be presented with abnormalities details.

## 9 CHANGE HISTORY

- Version 2 (dated 09 May 2018): Update of TFL to match ICH standard, removal of laboratory summary tables over time and new definitions for derived variables (First treatment administration as baseline value). Listing and tables for AEs subject to immediate reporting added following protocol version dated 22 December 2017.
- Version 3 (dated 12 December 2018): Addition of AFP listing (separated from urinalysis results) and listing for echocardiogram and Troponin level. Modification of treatment compliance definitions. Addition of imputation rules for partial birthdates if day is missing. Addition of rules for laboratory parameters intensity grade when normal limits are missing and addition of laboratory parameters to be graded according to CTCAE V4.03. Deletion of the listing of eligibility criteria for enrolled patients because of duplication with listing of protocol deviation at inclusion for enrolled patients. Deletion of tables of other safety data (vital signs, thyroid function, ECOG and ECG). Addition of listings with reason for exclusion from DLT population and PP population. Addition of formulas of calculated creatinine clearance (Cockcroft-Gault formula) and corrected calcium.

10 LIST OF TABLES, FIGURES AND LISTINGS

Confidential
Version 3.0 – 12DEC2018

Page 38/51

Confidential Version 3.0 – 12DEC2018

Page 39/51

Confidential Version 3.0 – 12DEC2018

Page 40/51

Confidential Version 3.0 – 12DEC2018

Page 41/51

[figure not shown]
Confidential Version 3.0 – 12DEC2018

Page 42/51

Confidential
Version 3.0 – 12DEC2018

TG6006.01 SAP

Page 43/51

